#### **6.4. Blinding**

This is an open-label study.

#### **6.5. Study Intervention Compliance**

When participants are dosed at the site (PF-07901801 and tafasitamab), they will receive study intervention directly from the investigator or designee, under medical supervision. The date and time of each dose administered in the clinic will be recorded in the source documents and recorded in the CRF. The dose of study intervention and study participant identification will be confirmed at the time of dosing by a member of the study site staff other than the person administering the study intervention.

The site will complete the required dosage Preparation Record located in the IP Manual. The use of the Preparation Record is preferred, but it does not preclude the use of an existing appropriate clinical site documentation system. The existing clinical site's documentation system should capture all pertinent/required information on the preparation and administration of the dose. This may be used in place of the Preparation Record after approval from the sponsor and/or designee.

When participants self-administer study lenalidomide at home, compliance with study intervention will be assessed at each visit. Compliance will be assessed by direct questioning, dosing diary (to be maintained while on lenalidomide), and counting returned tablets/capsules during the site visits and documented in the source documents and CRF. Participants will be required to return the completed patient dosing diary for lenalidomide on Day 1 of every cycle through Cycle 12 or EOT for timely review by site personnel and discussion of missed doses and/or compliance issues to ensure accurate data entry for the Dosing CRF.

A record of the number of PF-07901801 vials, tafasitamab vials, and lenalidomide capsules dispensed to and taken by each participant must be maintained and reconciled with study intervention and compliance records. Intervention start and stop dates, including dates for intervention interruptions and/or dose reductions, will also be recorded in the CRF.

## 6.6. Dose Modification

Criteria for dose modification due to toxicity and efficacy are presented in the following sections. PF-07901801 dose escalation/de-escalation is described in [Section 4.3.3](#).

Every effort should be made to administer study intervention on the planned dose and schedule. In the event of significant toxicity, dosing of PF-07901801 and tafasitamab may be modified as described below. In the event of multiple toxicities, dose modification should be based on the worst toxicity observed and attribution for the combination treatment.

Dosing modifications should be assigned to each product based on attribution to each component (ie, when compound A and B are combined and toxicity occurs and is attributed to compound A, a dose modification of compound A may be applicable but not necessarily to compound B). When toxicity may be attributed to all compounds (eg, neutropenia and thrombocytopenia), all therapies will be interrupted and upon recovery only lenalidomide will be re-started at a lower dose.

Participants are to be instructed to notify investigators at the first occurrence of any adverse symptom. In addition to dose modifications, investigators are encouraged to employ best supportive care according to local institutional clinical practices.

### 6.6.1. Dose-Modification Guidelines

All dose modifications should be based on the worst preceding toxicity and must be recorded on the CRF. Dose modifications for tafasitamab are further described in MINJUVI (tafasitamab) SmPC; for dose modifications regarding lenalidomide consult the Revlimid® SmPC.

[Table 6](#) through [Table 9](#) provide dose modifications in case of hematologic and non-hematologic toxicities. Permitted dose reductions for lenalidomide are outlined in [Table 10](#). When dosing is withheld based on the following criteria outlined below, clinical and laboratory re-evaluation should be repeated at least weekly or more frequently per institutional guidelines until the toxicity resolves as per toxicity recommendation; see also [Appendix 6](#) (Hy's law). In events where there are transient lab value abnormalities that, based on investigator assessment, are not clinically significant or are related to disease and not the drug, continuation of therapy without following the dose-modification guidelines is permissible.

No specific dose adjustments are recommended for grade 1 or 2 treatment-related toxicity. However, investigators should always manage their participants according to their medical judgment based on the particular clinical circumstances.

Once a lenalidomide dose has been reduced for a given participant, all subsequent cycles will be administered at that dose level, unless further dose reduction is required. Intraparticipant dose re-escalation is not allowed.

Participants in Phase 1b experiencing a DLT may reduce PF-07901801 dosing and resume at the next lower dose level (if applicable) once adequate recovery is achieved, and in the

opinion of the investigator and sponsor, the participant is benefiting from therapy. In Phase 2, PF-07901801 toxicities are managed only with dose interruption (not reduction, unless expressly agreed otherwise following discussion between the investigator and the sponsor).

Appropriate follow-up assessments must be done until adequate recovery occurs as assessed by the investigator. Criteria required before treatment can resume are described in [Section 6.6.2](#).

If the AE that led to the treatment interruption recovers within the same cycle, then re-dosing in that cycle is allowed. Doses omitted for toxicity are not replaced within the same cycle. The need for a lenalidomide dose reduction at the time of treatment resumption should be based on the criteria defined in the tables below, unless expressly agreed otherwise following discussion between the investigator and the sponsor. If a dose reduction of lenalidomide is applied in the same cycle, the participant will need to return to the clinic to receive new drug supply.

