**Table 7. Dose Modifications for Non-Hematologic Toxicities**

Criteria	Severity	Dosage modification
Non-hematologic laboratory events considered related to study treatment(s)	≥G3	

Hold suspected therapy(ies) until resolution to ≤G2 or baseline or to a level determined to be acceptable by the investigator.

Lenalidomide may be reduced by one dose level. See also SmPCs for MINJUVI (tafasitamab) and REVLIMID (lenalidomide).

Transient, asymptomatic, G4 laboratory abnormalities considered not clinically significant may not require a dose reduction following agreement between investigator and the sponsor.

Abnormal liver tests (related or unrelated)	≥G2	

Participants who present with elevated AST/ALT and bilirubin must be evaluated further as potential DILI (Hy's law) cases to definitively determine the etiology of the abnormal laboratory values; evaluation is to occur as soon as possible, preferably within 48 hours of the abnormal results. See Liver Safety Guidelines for follow-up of possible DILI (Appendix 6).

Abnormal liver tests (related or unrelated)	≥G3	

Hold suspected therapy(ies) until resolution to ≤G2 or baseline or to a level determined to be acceptable by the investigator.

Lenalidomide may be reduced by one dose level. See also SmPCs for MINJUVI (tafasitamab) and REVLIMID (lenalidomide).

Participants who present with elevated AST/ALT and bilirubin must be evaluated further as potential DILI (Hy's law) cases to definitively determine the etiology of the abnormal laboratory values; evaluation is to occur as soon as possible, preferably within 48 hours of the abnormal results. See Liver Safety Guidelines for follow-up of possible DILI (Appendix 6).

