**Table 8. Dose Modifications for Lenalidomide Toxicities**

Criteria	Severity	Dosage modification
Tumor flare reaction (related)  Kidney toxicities as per CTCAE v5.0 (test can be repeated after proper hydration, if needed) (related or unrelated)	G3/4	
 
Interrupt lenalidomide dosing.
 
Provide symptomatic treatment as per local guidelines.
 
Continue other study interventions after discussion with the sponsor.
 

	Toxicities resolve to $\leq$ G1	
 
Restart lenalidomide (maintain same dose level).
 

	G2	
 
Reduce lenalidomide to 10 mg once daily.
 

	G3 not requiring dialysis	
 
Administer lenalidomide at 15 mg every other day.
 
Discontinue lenalidomide if dialysis is required.
 

	G4	
 
Discontinue lenalidomide.
 

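### The Section 6.6.1 exception for transient laboratory values lets the investigator alone set aside the Table 8 kidney dose rules for lenalidomide, which apply whatever the cause

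*Protocol*

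**What the plan says.** Section 6.6.1 of the protocol points to Tables 6 to 9 for dose modifications and then makes an exception. Where the investigator assesses a transient laboratory abnormality as "not clinically significant or are related to disease and not the drug, continuation of therapy without following the dose-modification guidelines is permissible". The sentence gives the sponsor no role, sets no grade limit, excludes no table row, does not define transient, and does not say which text prevails if a table row points the other way.

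The kidney entry in Table 8 is headed "Kidney toxicities as per CTCAE v5.0 (test can be repeated after proper hydration, if needed) (related or unrelated". It changes lenalidomide only:
- G2: 10 mg once daily.
- G3 without dialysis: "Administer lenalidomide at 15 mg every other day".
- G4, or any need for dialysis: stop lenalidomide.

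Two other sentences in 6.6.1 matter here. One reads "No specific dose adjustments are recommended for grade 1 or 2 treatment-related toxicity". The other, on lenalidomide, reads "Intraparticipant dose re-escalation is not allowed".

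Two provisions elsewhere narrow the question. Section 6.1.1.3 puts participants with creatinine clearance of 30 to <60 mL/min on 10 mg daily. Section 6.6.2 bars re-treatment after an interruption, or at the start of a cycle, until treatment-related non-hematologic laboratory toxicity is back to baseline or to G2 or lower.

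**The concern.** Table 8 ignores cause for a good reason. Section 2.2.3.3.3 says that about 82% of a lenalidomide dose leaves in the urine, mostly unchanged, and that drug clearance falls with creatinine clearance. Exposure therefore rises when renal function falls, whether the lymphoma, tumor lysis or a study drug is responsible. Section 4.3.2 gives the higher exposure, with its hematologic and hepatic risk, as the reason for keeping participants below 60 mL/min out of Phase 1b.

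The 6.6.1 exception turns on cause, or on one investigator's view of clinical significance. Faced with a transient, disease-related G3 creatinine value, one site could cut to 15 mg every other day under Table 8. Another could stay at 25 mg under 6.6.1. Both could claim to follow the protocol. It would also be unclear whether the second site had a medication error under Section 8.4.10, which counts failure to make a dose change that the protocol requires.

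**Working it through.** **Step 1: which kidney values remain open?**

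| Situation | Text that governs | Open? |
|---|---|---|
| Clearance 30 to <60 mL/min | 6.1.1.3: 10 mg daily; it lies outside the guidelines that 6.6.1 waives | No |
| Treatment-related value above G2 (and above baseline) at a new cycle | 6.6.2 blocks dosing | No |
| G3 or G4 value within a cycle | Table 8, which 6.6.1 permits the investigator not to follow | Yes |
| Disease-related G3 or G4 value at a new cycle | As above; 6.6.2 covers treatment-related values only | Yes |

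**Step 2: size while clearance is low.** Inputs:
- Full dose 25 mg daily on Days 1 to 21 (Section 6.1.1.3).
- AUC proportional to dose from 5 to 400 mg (Section 2.2.3.3.3).
- A 75% fall in drug clearance in severe renal impairment (same section), so 0.25 remains.
- Assumption: the Table 8 G3 row corresponds to severe impairment. The documents do not give the grade limits.

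AUC relative to 25 mg with normal function = (average daily dose / 25) / remaining clearance.
- Staying at 25 mg: 1.00 / 0.25 = 4.0.
- Table 8 G3 dose, 15 mg every other day = 7.5 mg per day: 0.30 / 0.25 = 1.2.
- Already on 10 mg daily: 0.40 / 0.25 = 1.6.
- Table 8 G4 row: lenalidomide stops, so the comparison is with no further dosing.

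**Step 3: size over a cycle.** If clearance is 75% down for d of the 21 dosing days and the dose stays at 25 mg, average relative AUC = [(21 − d) + 4.0d] / 21. The durations are assumed.
- d = 3: 30/21 = 1.4.
- d = 7: 42/21 = 2.0.
- d = 14: 63/21 = 3.0, although two weeks stretches the word transient.

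**Step 4: grade 1 or 2 sentence.** It says that no specific adjustment is recommended for treatment-related toxicity of those grades. The Table 8 kidney G2 row reduces lenalidomide to 10 mg, and the Table 9 G2 row has the infusion interrupted at once. Both rows cover treatment-related events, so the sentence and the tables disagree.

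**Step 5: what strict use of Table 8 costs.** Planned lenalidomide per cycle is 25 × 21 = 525 mg. Taking 15 mg on Days 1, 3, …, 21 is 11 doses, or 165 mg, and 165/525 = 31%. Because 6.6.1 forbids re-escalation, a participant whose kidney function recovers would stay there. The only upward step in the protocol is the 15 mg daily option in 6.1.1.3, for moderate impairment.

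**The case against.** The best defence is that a specific row naturally governs over a general permission, and that the kidney row deals with transience itself by allowing a repeat test after hydration. Section 8.3.4 adds laboratory review before infusions, repetition of clinically significant values, and notice to the sponsor if they do not recover in reasonable time. Section 6.1.1.3 also requires lenalidomide to be given according to the Revlimid SmPC, and 6.6.1 refers sites to it for dose modification.

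Part of this stands. The SmPC may supply a rule below 30 mL/min, but its content is not in the documents, so that cannot be confirmed. Section 8.3.4 limits how long a value can go unnoticed but sets no dose. As to precedence, none is stated, and the exception expressly permits departure from the guidelines that contain the row.

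A reader might infer a wider problem in four ways that the documents do not support:
- **Liver rows.** The Table 7 heading "Abnormal liver tests (related or unrelated" looks like a parallel case. But the action at G3 and above is to hold the suspected therapy, and nothing is suspected when the cause is disease. The investigator may also end the hold at a level they accept. The Appendix 6 liver work-up stands apart.
- **Sponsor agreement for G4 values.** Table 7 says such values "may not require a dose reduction following agreement between investigator and the sponsor". Lenalidomide reduction in that row is already optional, so the clause exempts sites from something the row does not require.
- **Two standards within 6.6.1.** The need for a lenalidomide reduction on resumption "should be based on the criteria defined in the tables below, unless expressly agreed otherwise following discussion between the investigator and the sponsor". That concerns restarting after an interruption. The exception concerns values for which dosing never stopped.
- **A second exposure figure.** Section 2.2.3.3.3 also gives a 66% fall in clearance. On its natural reading that is moderate impairment, which 6.1.1.3 already cuts to 10 mg.

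**Conclusion.** The conflict is real and confined to the kidney rows, mainly at G3 and G4, together with the grade 1 or 2 sentence. For an affected participant, exposure would be about 4.0 times normal rather than about 1.2 times while the fall lasts, or 1.6 times if already on 10 mg. These figures rest on linear kinetics and on equating G3 with severe impairment. The 4.0 also supposes a drop straight from at least 60 to below 30 mL/min while still on 25 mg.

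The documents give no rate for such values, so the number affected is unknown. It is small: about 20 participants were planned for Phase 1b (Section 4.1), entry required clearance of at least 60 mL/min (Section 5.1), lenalidomide runs for at most 12 cycles, and Phase 2 will not start. The text still governs anyone who continues on lenalidomide under Section 10.1.10 after the termination. Nothing in the documents shows that any participant was overexposed. This is a minor point and a cheap improvement.

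**What to change.** Add to the 6.6.1 exception: *This exception does not apply to the kidney rows of Table 8, which are followed whatever the cause after the repeat test the row allows; after recovery the earlier lenalidomide dose may be resumed if the investigator and sponsor agree, as an exception to the no re-escalation rule.*

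Begin the grade 1 or 2 sentence with: *Except where Tables 7 to 9 give an action for that grade,*

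The cost is one added sentence and one lead-in, by administrative letter or amendment, with no new data or procedures. The downside is that a transient, disease-caused kidney value that persists on repeat now forces a lenalidomide cut. The resumption clause keeps that from becoming a permanent drop to 31% of the planned dose, at the price of one sponsor discussion per participant who recovers.

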#### 2.2.3.3.3. Lenalidomide

Lenalidomide is rapidly absorbed following oral administration with a median serum  $T_{max}$  ranging from 0.5 to 1 hour with >90% oral bioavailability. Lenalidomide AUC and  $C_{max}$  values increased proportionally with dose from 5 mg to 400 mg indicating linear PK.

Coadministration of lenalidomide with a high-fat meal reduced the extent and rate of lenalidomide oral absorption, however, the effect of food was considered not clinically significant, and thus lenalidomide can be taken with or without food. The mean half-life of lenalidomide is 3 to 5 hours in participants with MM.

Lenalidomide binding to plasma proteins is approximately 30% and the apparent volume of distribution is 74-91 L. Lenalidomide is also present in semen after the administration of a 25 mg QD dose. However, the lenalidomide total amount of drug presented in semen over 72 hours was <0.01%.

Lenalidomide is eliminated primarily via renal clearance with ~82% of the dose excreted in urine, predominantly as unchanged drug. Lenalidomide renal excretion was not saturable over the dose range of 5 mg to 400 mg. Dose adjustment is needed for patients with renal impairment. As creatinine clearance decreases, half-life increases, and drug clearance decreases linearly. In a dedicated renal impairment study, participants with moderate and severe impairment had a 3-fold increase in half-life and a 66% to 75% decrease, respectively, in drug clearance compared to healthy participants. For Phase 2 participants with moderate renal impairment (creatinine clearance  $\geq$ 30 mL/min and <60 mL/min), lenalidomide will be started (and/or reduced) to 10 mg daily (see [Section 6.1.1.3](#)).

Lenalidomide undergoes limited metabolism. Mild hepatic impairment ( $T_{bili} > 1-1.5 \times ULN$  or  $AST > ULN$ ) did not have a clinically significant effect on the PK of lenalidomide. Additionally, age (39 to 85 years), body weight (33 to 135 kg), sex, and race did not have a clinically relevant effect on lenalidomide clearance in adult participants.

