##### **4.3.2. Dosing regimen of Tafasitamab and Lenalidomide**

Tafasitamab will be administered at 12 mg/kg IV according to the following schedule; each cycle has 28 days.

- C1: Days 1, 4, 8, 15 and 22.

- C2 and C3 (QW): Days 1, 8, 15 and 22.
- $\geq$ C4 (Q2W): Days 1 and 15.

This is the recommended dosage and dosing schedule in the USPI and EU SmPC of tafasitamab in combination with lenalidomide for the treatment of adult patients with R/R DLBCL, who are not eligible for ASCT.

Lenalidomide will be administered 25 mg PO daily on Days 1 through 21 of each 28-day cycle for up to 12 cycles. This is the dosage regimen used in the L-MIND study, which supported the accelerated and conditional approval of tafasitamab in combination with lenalidomide for the treatment of adult patients with R/R DLBCL NOS, including DLBCL arising from low grade lymphoma, and who are not eligible for ASCT. To reduce PK and safety assessment variability, participants with creatinine clearance  $<60$  mL/min will be excluded in the Phase 1b of the study since lenalidomide exposure and the risk for higher hematological adverse reactions or hepatotoxicity increase in this population.

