#### 6.1.1.3. Lenalidomide

Lenalidomide will be administered according to instructions in the current Revlimid SmPC.

Starting on C1D1, lenalidomide will be administered 25 mg PO daily on Days 1 through 21 of each 28-day cycle for up to 12 cycles.

On C1D1, C2D1, C3D1, C4D1, the daily dose of lenalidomide is to be taken at the clinic after the blood draw for lenalidomide PK and prior to the PF-07901801 IV infusion (See [SoA](#)).

Lenalidomide is primarily excreted by the kidney; participants with greater degrees of renal impairment can have impaired treatment tolerance. For participants with moderate renal impairment (creatinine clearance  $\geq 30$  mL/min and  $< 60$  mL/min), lenalidomide will be started (and/or reduced) to 10 mg daily. The dose may be escalated to 15 mg QD after 2 cycles if participant is not responding to treatment and is tolerating the treatment.

Participants may take their oral doses of lenalidomide without regard to food.

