**Table 10. Reductions for Lenalidomide**

Starting dose	25 mg
DL1	20 mg
DL2	15 mg
DL3 (starting dose for moderate renal impairment)	10 mg
DL4	5 mg
DL5 a	2.5 mg

a. Patients who cannot tolerate DL5 are to be discontinued from lenalidomide treatment in the study but should continue PF-07901801 and tafasitamab.

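### Protocol 6.1.1.3 permits lenalidomide to rise from 10 mg to 15 mg after a renal reduction, 6.6.1 forbids any re-escalation, and nothing says which governs or in which phase

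*Protocol*

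**What the plan says.** **Protocol 6.1.1.3 (Lenalidomide).** For creatinine clearance of at least 30 and below 60 mL/min, "lenalidomide will be started (and/or reduced) to 10 mg daily". It continues: "The dose may be escalated to 15 mg QD after 2 cycles if participant is not responding to treatment and is tolerating the treatment". No phase is named.

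**Protocol 6.6.1 (Dose-Modification Guidelines).** "Once a lenalidomide dose has been reduced for a given participant, all subsequent cycles will be administered at that dose level", with further reduction as the only stated departure. The next sentence is "Intraparticipant dose re-escalation is not allowed". No renal exception is given.

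**Protocol Table 8**, one of the dose-modification tables under 6.6.1. For Grade 2 kidney toxicity, related or unrelated: "Reduce lenalidomide to 10 mg once daily". No later increase is mentioned.

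**Protocol Table 10.** 15 mg is DL2 and 10 mg is DL3, and the 10 mg row is marked as the starting dose in moderate renal impairment.

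**Phase limits.** Section 2.2.3.3.3 gives the same renal rule but opens with "For Phase 2 participants with moderate renal impairment" and points to 6.1.1.3. The Section 5.1 note on a 10 mg start is also headed as a Phase 2 note. Section 4.3.2 says that participants with clearance below 60 "mL/min will be excluded in the Phase 1b of the study". Amendment 2 records that Phase 2 will not be initiated.

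**The concern.** For a participant brought down to 10 mg during treatment because of renal function, one section allows a step that the other rules out, and the protocol gives no order of precedence. Two sites could each follow the protocol and give different doses to participants in the same situation. Section 4.3.2 itself describes the population as having higher lenalidomide exposure and a higher risk of hematological reactions and hepatotoxicity.

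It also affects how a dose is classified. Section 8.4.10 counts an incorrect dosage (±20%) as a medication error, to be recorded and notified to the sponsor. Going from 10 mg to 15 mg is a 50% change, so the same administration could be a permitted dose under 6.1.1.3 and an error under 6.6.1.

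**Working it through.** The documents give no figure to reproduce. The check sets the two rules against each way of arriving at 10 mg.

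| How the participant comes to be on 10 mg | Section 6.1.1.3 | Section 6.6.1 | Conflict? |
|---|---|---|---|
| Starts at 10 mg for renal impairment | 15 mg permitted, on conditions | Bars going back up after a reduction; none has occurred | Not clearly |
| Reduced on treatment because clearance falls into the 30 to <60 mL/min band | 15 mg permitted, on conditions | Stays at 10 mg | Yes |
| Reduced under Table 8 for Grade 2 kidney toxicity | Not stated whether this counts as a renal reduction | Stays at 10 mg | Only if 6.1.1.3 is meant to cover it |
| Reduced for another toxicity, clearance 60 mL/min or more | Does not apply | Stays at 10 mg | No |

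**Is the second row within 6.1.1.3?** Yes. The words in brackets in "lenalidomide will be started (and/or reduced) to 10 mg daily" bring in participants already on treatment. The Section 5.1 note, by contrast, speaks only of starting at the reduced dose.

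**Is there an exception elsewhere?** None was found. Section 6.6.1 does let the investigator and sponsor agree otherwise, but for lenalidomide that wording concerns whether a reduction is needed when treatment resumes, not a later increase.

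**Who can be in the second row?** With Phase 2 not opening, only Phase 1b participants. They enter with clearance of at least 60 mL/min, so a renal 10 mg dose can arise only through decline on treatment. The conflict then bites only if the participant has completed 2 cycles, is not responding, is tolerating treatment, and is still within the 12-cycle limit. If the 2 cycles are counted from the reduction (an assumption, since the text does not say), the reduction must be in place by Cycle 12 − 2 = 10 for any cycle at 15 mg to remain.

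**Size of the difference for such a participant:**

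- Dose ratio: 15/10 = 1.5.
- Full cycle at 10 mg: 10 × 21 = 210 mg.
- Full cycle at 15 mg: 15 × 21 = 315 mg.
- Against the intended 525 mg per 4-week cycle in SAP 6.6.3.3: 210/525 = 40% and 315/525 = 60%.

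**The case against.** Four arguments have force.

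1. **The renal rule is a Phase 2 rule.** Section 2.2.3.3.3 uses the same bracketed phrase, limits it to Phase 2 and refers to 6.1.1.3; the 5.1 note is also for Phase 2; and Phase 1b excludes clearance below 60 mL/min. This reading is plausible and, with Phase 2 cancelled, would leave nobody affected. But 6.1.1.3, the section that sites dose from, does not state the limit. Even read as Phase 2 only, the text still contradicts 6.6.1 for reduced participants.
2. **The specific rule overrides the general one.** Section 6.6.1 is framed around toxicity, while 6.1.1.3 sets the dose by clearance band, so the latter could be an exception. That is a reasonable reading, but the protocol does not state it and the prohibition is unqualified.
3. **Nobody is forced to break a rule.** The 15 mg step is optional, and remaining at 10 mg satisfies both sections. That is correct, but only because the participant forgoes something that 6.1.1.3 grants.
4. **The lenalidomide product information may settle it.** Both sections refer to it. It is not among the documents, so this cannot be judged here.

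What stands is that the conflict is narrow and concerns a permission rather than two opposed orders. None of the four points removes it.

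**Conclusion.** The inconsistency is real and confined to participants reduced to 10 mg on treatment for renal function. A second ambiguity is whether the renal rule applies in Phase 1b at all. The documents give no count of affected participants; out of about 20 planned for Phase 1b it is likely small and may be zero. Where the conflict does arise, the doses differ by 50%. It can still matter after termination, because Section 10.1.10 lets participants continue study intervention when the reason for stopping is unrelated to safety.

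Three stronger readings are tempting but unsupported:

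- **That every participant reduced for renal function is affected.** The 15 mg step also requires 2 cycles, non-response and tolerance.
- **That the SAP's dose-reduction summaries become inconsistent.** SAP 6.6.3.4 counts a change to a lower non-zero level than planned. A participant taken from 25 mg to 10 mg is counted once either way, and a later rise to 15 mg is not a new reduction. Relative dose intensity is built on the dose actually given, so it would reflect whichever dose was used.
- **That a Table 8 kidney reduction is necessarily a 6.1.1.3 reduction.** Table 8 is triggered by CTCAE grade and 6.1.1.3 by a clearance band, and the protocol does not equate them.

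**What to change.** Reconcile Sections 2.2.3.3.3, 6.1.1.3 and 6.6.1 and Table 8 by stating:

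- whether the 15 mg step in 6.1.1.3 is an exception to the 6.6.1 prohibition;
- in which phase, and for which participants (starting at 10 mg, reduced to it, or both), it applies;
- whether a reduction to 10 mg under the Table 8 kidney-toxicity rows falls under it.

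No view is taken on which rule is right; that is for the sponsor's clinical team. The cost is a sentence or two and a cross-reference in each direction, with no change to design, sample size or analysis.
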